7. HEALTH ECONOMICS

Not applicable.

8. SAFETY

The investigator or site staff is/are responsible for the detection, documentation and reporting of events meeting the criteria and definition of an AE or SAE as provided in this protocol.

Each subject's parent(s)/LAR(s) will be instructed to contact the investigator immediately should the subject manifest any signs or symptoms they perceive as serious.

8.1. Safety definitions

8.1.1. Definition of an adverse event

An AE is any untoward medical occurrence in a clinical investigation subject, temporally associated with the use of a medicinal product, whether or not considered related to the medicinal product.

An AE can therefore be any unfavourable and unintended sign (including an abnormal laboratory finding), symptom, or disease (new or exacerbated) temporally associated with

the use of a medicinal product. For marketed medicinal products, this also includes failure to produce expected benefits (i.e. lack of efficacy), abuse or misuse.

Examples of an AE include:

- Significant or unexpected worsening or exacerbation of the condition/indication under study.
- New conditions detected or diagnosed after investigational vaccine even though they may have been present prior to the start of the study.
- Signs, symptoms, or the clinical sequelae of a suspected interaction.
- Signs, symptoms, or the clinical sequelae of a suspected overdose of either investigational vaccine or a concurrent medication (overdose per se should not be reported as an AE/SAE).
- Signs, symptoms temporally associated with vaccine administration.
- Significant failure of expected pharmacological or biological action.
- Pre- or post-treatment events that occur as a result of protocol-mandated procedures (i.e. invasive procedures, modification of subject's previous therapeutic regimen).

AEs to be recorded as endpoints (solicited AEs) are described in Section 8.1.3. All other AEs will be recorded as UNSOLICITED AEs.

Examples of an AE DO NOT include:

- Medical or surgical procedures (e.g. endoscopy, appendectomy); the condition that leads to the procedure is an AE/SAE.
- Situations where an untoward medical occurrence did not occur (e.g. social and/or convenience admission to a hospital, admission for routine examination).
- Anticipated day-to-day fluctuations of pre-existing disease(s) or condition(s) present or detected at the start of the study that do not worsen.
- Pre-existing conditions or signs and/or symptoms present in a subject prior to the first study vaccination. These events will be recorded in the medical history section of the eCRF.

8.1.2. Definition of a serious adverse event

A SAE is any untoward medical occurrence that:

- a. Results in death,
- b. Is life-threatening,

Note: The term 'life-threatening' in the definition of 'serious' refers to an event in which the subject was at risk of death at the time of the event. It does not refer to an event, which hypothetically might have caused death, had it been more severe.

- c. Requires hospitalisation or prolongation of existing hospitalisation,

Note: In general, hospitalisation signifies that the subject has been admitted at the hospital or emergency ward for observation and/or treatment that would not have been appropriate in the physician’s office or in an out-patient setting. Complications that occur during hospitalisation are also considered AEs. If a complication prolongs hospitalisation or fulfils any other serious criteria, the event will also be considered serious. When in doubt as to whether ‘hospitalisation’ occurred or was necessary, the AE should be considered serious.

Hospitalisation for elective treatment of a pre-existing condition (known or diagnosed prior to informed consent signature) that did not worsen from baseline is NOT considered an AE.

- d. Results in disability/incapacity.

Note: The term disability means a substantial disruption of a person’s ability to conduct normal life functions. This definition is not intended to include experiences of relatively minor medical significance such as uncomplicated headache, nausea, vomiting, diarrhoea, influenza like illness, and accidental trauma (e.g. sprained ankle) which may interfere or prevent everyday life functions but do not constitute a substantial disruption.

Medical or scientific judgement should be exercised in deciding whether reporting is appropriate in other situations, such as important medical events that may not be immediately life-threatening or result in death or hospitalisation but may jeopardise the subject or may require medical or surgical intervention to prevent one of the other outcomes listed in the above definition. These should also be considered serious. Examples of such events are invasive or malignant cancers, intensive treatment in an emergency room or at home for allergic bronchospasm, blood dyscrasias or convulsions that do not result in hospitalisation.

8.1.3. Solicited adverse events

8.1.3.1. Solicited local (injection-site) adverse events

The following local (injection-site) AEs will be solicited:

Table 15 Solicited local adverse events

Pain at injection site
Redness at injection site
Swelling at injection site

8.1.3.2. Solicited general adverse events

The following general AEs will be solicited:

Table 16 Solicited general adverse events

Drowsiness
Fever
Irritability/Fussiness
Loss of appetite

Note: Temperature will be recorded in the evening. Should additional temperature measurements be performed at other times of day, the highest temperature will be recorded in the eCRF.

8.1.4. Clinical laboratory parameters and other abnormal assessments qualifying as adverse events or serious adverse events

In absence of diagnosis, abnormal laboratory findings (e.g. clinical chemistry, haematology, urinalysis) or other abnormal assessments (e.g. vital signs etc) that are judged by the investigator to be clinically significant will be recorded as AE or SAE if they meet the definition of an AE or SAE (refer to Sections 8.1.1 and 8.1.2). Clinically significant abnormal laboratory findings or other abnormal assessments that are present at baseline and significantly worsen following the start of the study will also be reported as AEs or SAEs. However, clinically significant abnormal laboratory findings or other abnormal assessments that are associated with the disease being studied, unless judged by the investigator as more severe than expected for the subject's condition, or that are present or detected at the start of the study and do not worsen, will not be reported as AEs or SAEs.

The investigator will exercise his or her medical and scientific judgement in deciding whether an abnormal laboratory finding or other abnormal assessment is clinically significant.

8.2. Detecting and recording adverse events, serious adverse events**8.2.1. Time period for detecting and recording adverse events and serious adverse events**

All AEs starting within 30 days following administration of each dose of study vaccine (Day 0 to Day 30) must be recorded into the appropriate section of the eCRF irrespective of intensity or whether or not they are considered vaccination-related.

The time period for collecting and recording SAEs will begin at the first receipt of study vaccine and will end 30 days following administration of the last dose of study vaccine for each subject. See Section 8.3 for instructions on reporting of SAEs.

All AEs/SAEs leading to withdrawal from the study will be collected and recorded from the time of the first receipt of study vaccine.

SAEs that are related to the investigational vaccine will be collected and recorded from the time of the first receipt of study vaccine until the subject is discharged from the study.

In addition to the above-mentioned reporting requirements and in order to fulfil international reporting obligations, SAEs that are related to study participation (i.e. protocol-mandated procedures, invasive tests, a change from existing therapy) or are related to a concurrent GSK medication/vaccine will be collected and recorded from the time the subjects' parent(s)/LAR(s) consents to their child/wards participation in the study until she/he is discharged from the study.

An overview of the protocol-required reporting periods for AEs and SAEs is given in [Table 17](#), [Table 18](#) and [Table 19](#). (Amended 06 September 2016)

Table 17 Reporting periods for adverse events and serious adverse events for subjects vaccinated with *Infanrix hexa* at 2, 4 and 6 months of age (Amended 06 September 2016)

Event	Pre-V1*	V1	3 d post V1	30 d post -V1	V2	3 d post V2	30 d post-V2	V3	3 d post V3	30 d post-V3	V4 Study Conclusion			
		D0		D 30	M2			M 4			M5			
Solicited local and general AEs														
Unsolicited AEs														
AEs/SAEs leading to withdrawal from the study														
SAEs†														
SAEs related to study participation or concurrent GSK medication/vaccine†														

* i.e. consent obtained. Pre-V: pre-vaccination; V: vaccination; Post-V: post-vaccination; D: Day, M: Month

† AEs/SAEs reported from the administration of first dose of primary vaccination until the end of study will be recorded and analysed in this study (i.e. a part of 201330 [DTPA (BOOSTRIX)-048 PRI] study).

Table 18 Reporting periods for adverse events and serious adverse events for subjects vaccinated with *Infanrix hexa* at 2, 3 and 4 months of age (Amended 06 September 2016)

Event	Pre-V1*	V1	3 d post V1	30 d post -V1	V2	3 d post V2	30 d post-V2	V3	3 d post V3	30 d post-V3	V4 Study Conclusion			
		D0		D 30	M1			M2			M3			
Solicited local and general AEs														
Unsolicited AEs														
AEs/SAEs leading to withdrawal from the study														
SAEs†														
SAEs related to study participation or concurrent GSK medication/vaccine†														

* i.e. consent obtained. Pre-V: pre-vaccination; V: vaccination; Post-V: post-vaccination; D: Day, M: Month

† AEs/SAEs reported from the administration of first dose of primary vaccination until the end of study will be recorded and analysed in this study (i.e. a part of 201330 [DTPA (BOOSTRIX)-048 PRI] study).

Table 19 Reporting periods for adverse events and serious adverse events for subjects vaccinated with Infanrix hexa at 2 and 4 months of age or at 3 and 5 months of age (Amended 06 September 2016)

Event	Pre-V1*	V1	3 d post V1	30 d post-V1	V2	3 d post V2	30 d post-V2	V4 Study Conclusion					
		D0		D 30		M2			M3				
Solicited local and general AEs													
Unsolicited AEs													
AEs/SAEs leading to withdrawal from the study													
SAEs†													
SAEs related to study participation or concurrent GSK medication/vaccine†													

* i.e. consent obtained. Pre-V: pre-vaccination; V: vaccination; Post-V: post-vaccination; D: Day, M: Month
† AEs/SAEs reported from the administration of first dose of primary vaccination until the end of study will be recorded and analysed in this study (i.e. a part of 201330 [DTPA (BOOSTRIX)-048 PRI] study).

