3. STUDY DESIGN OVERVIEW

Figure 1 Study design diagram for infants receiving a 3-dose schedule of *Infanrix hexa* (Amended 06 September 2016)

N: Maximum number of subjects planned to be enrolled

M = Month, Mo = age in months

[figure not shown]
Timepoints have been numbered based on the different vaccination schedules. D0, M1, M2 and M3 timepoints reflect for subjects who will be vaccinated according to the 2, 3 and 4 month schedule while D0, M2, M4 and M5 timepoints reflect for subjects who will be vaccinated according to the 2, 4 and 6 month schedule.

* In some countries/regions **with an *Infanrix hexa* 3-dose schedule**, *Prevenar 13* is given as a 2-dose schedule at 2 and 4 months of age as a part of the routine immunisation programme

Pre-Pri = Blood sample to be collected before the first dose of the primary vaccination course

Post-Pri = Blood sample to be collected one month after the last dose of the primary vaccination course

Figure 2 Study design diagram for infants receiving a 2-dose schedule of Infanrix hexa (Amended 06 September 2016)

N: Maximum number of subjects planned to be enrolled

M = Month, Mo = age in months

Pre-Pri = Blood sample to be collected before the first dose of the primary vaccination course

Post-Pri = Blood sample to be collected one month after the last dose of the primary vaccination course

Subjects will be vaccinated either at 2 and 4 months of age or 3 and 5 months of age, according to the routine national immunisation schedule

Protocol waivers or exemptions are not allowed with the exception of immediate safety concerns. Therefore, adherence to the study design requirements, including those specified in the outline of study procedures (Section 5.5), are essential and required for study conduct.

- Experimental design: Phase IV, open-label, non-randomised, multi-centric, multi-country study with two parallel groups.
- Duration of the study: The intended duration of the study is approximately 3 months, per subject, for subjects vaccinated according to **the 2 and 4, the 3 and 5 or the 2, 3 and 4 months schedule** and approximately 5 months, per subject, for those vaccinated according to 2, 4 and 6 month schedule. **(Amended 06 September 2016)**
 - Epoch 001: Primary starting at Visit 1 (Day 0) and ending at Visit 4 (Month **3 or 5, depending on the vaccination schedule**). **(Amended 06 September 2016)**

- **End of Study (EoS):** Last testing results released of samples collected at Visit 4.

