10.2. Secondary endpoints

- Persistence of antibodies before the first dose of *Infanrix hexa*.
 - Anti-diphtheria and anti-tetanus seroprotection status, anti-PT, anti-FHA, anti-PRN seropositivity status and antibody concentrations.
- Immunogenicity with respect to components of *Infanrix hexa* and *Prevenar 13*.
 - Anti-diphtheria, anti-tetanus, anti-poliovirus type 1, anti-poliovirus type 2, anti-poliovirus type 3, anti-HBs, anti-PRP, anti-PT, anti-FHA, anti-PRN and anti-pneumococcal serotypes (1, 3, 4, 5, 6A, 6B, 7F, 9V, 14, 18C, 19A, 19F, 23F) antibody concentrations or titres, one month after the last dose of primary vaccination.
- Immunogenicity with respect to components of *Infanrix hexa*.
 - Anti-PT, anti-FHA, anti-PRN antibody seropositivity status, one month after the last dose of primary vaccination.
- Solicited local and general symptoms.
 - Occurrence of solicited local/general symptoms during the 4-day (Day 0-Day 3) follow-up period after each vaccination.
- Unsolicited adverse events.
 - Occurrence of unsolicited symptoms during the 31-day (Day 0-Day 30) follow-up period after each vaccination.
- Serious adverse events.
 - Occurrence of SAEs from first vaccination dose to study end.

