- The verbatim reports of unsolicited AEs will be reviewed by a physician and the signs and symptoms will be coded according to MedDRA. Every verbatim term will be matched with the appropriate Preferred Term. The percentage of subjects with unsolicited AEs occurring within 31-day (Day 0- Day 30) follow-up period after any dose with its exact 95% CI [Clopper, 1934] will be tabulated by group, and by preferred term. Similar tabulation will be done for unsolicited AEs rated as grade 3, for unsolicited AEs with causal relationship to vaccination and AEs/SAEs leading to withdrawal from the study.
- The percentage of subjects who receive concomitant medication and antipyretic medication during the 4-day (Day 0- Day 3) follow-up period and the 31-day follow-up (Day 0 – Day 30) will be tabulated (with exact 95% CI [Clopper, 1934]) after each vaccine dose and overall.
- SAEs reported from first vaccination dose up to study end will be described in detail.
- Withdrawal due to AEs and SAEs following vaccinations will be described in detail.

Handling of missing data:

- For a given subject and the analysis of solicited AEs 4 days post-vaccination, missing or non-evaluable measurements will not be replaced. Therefore, the analysis of the solicited AEs based on the TVC will include only vaccinated subjects and doses with documented safety data (i.e. symptom screen completed).
- For analysis of unsolicited AEs, such as SAEs or AEs by primary Medical Dictionary for Regulatory Activities (MedDRA) term, and for the analysis of concomitant medications, all vaccinated subjects will be considered. Subjects, who do not report the event or the concomitant medication, will be considered as subjects without the event or the concomitant medication, respectively.
- For summaries reporting both solicited and unsolicited AEs, all vaccinated subjects will be considered. Subjects, who do not report the event or the concomitant medication, will be considered as subjects without the event or the concomitant medication, respectively.

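### The SAE endpoint and analysis run to an undefined study end, but general SAE collection stops 30 days after the last dose, so late unrelated SAEs can be missed and counted as no event

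*Protocol*

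**What the plan says.** **Collection.** Under Protocol Section 8.2.1, general SAE recording starts at the first study vaccine and "will end 30 days following administration of the last dose of study vaccine for each subject". The same section treats three classes differently:
- SAEs related to the investigational vaccine are collected "from the time of the first receipt of study vaccine until the subject is discharged from the study".
- SAEs related to study participation or to a concurrent product of the sponsor are collected from the time the parent "consents to their child/wards participation in the study until she/he is discharged from the study".
- For withdrawals: "All AEs/SAEs leading to withdrawal from the study will be collected and recorded from the time of the first receipt of study vaccine". No day-30 limit is given.

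The footnote to the SAE rows of Tables 17 to 19, also in Section 8.2.1, has no day-30 limit either: "AEs/SAEs reported from the administration of first dose of primary vaccination until the end of study will be recorded and analysed in this study".

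**Endpoint and analysis.** Protocol 10.2 and SAP 4.2 define the endpoint as "Occurrence of SAEs from first vaccination dose to study end". SAP 6.4.1 follows: "SAEs reported from first vaccination dose up to study end will be described in detail". The title of SAP Template 21 uses the same end.

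**What the end means.** Protocol Section 3 and SAP Section 2 define End of Study as "Last testing results released of samples collected at Visit 4", and the glossary allows this up to 8 months after the last subject's last visit. Protocol 9.3 instead equates the end of the study with the study conclusion visit. The SAE endpoint does not say which applies.

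**Visit 4 and unreported events.** Protocol Tables 6 to 9 allow Visit 4 on days 21 to 48 after the last dose, with day 30 as the optimum. Protocol 10.5 and SAP 6.4.1 keep all vaccinated infants in the SAE denominator and treat those with no reported event as not having had one.

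**The concern.** A site cannot follow all of these rules at once. Take an infant admitted to hospital on day 40 after the last dose for a cause judged unrelated, with Visit 4 on day 45. The main sentence of 8.2.1 says that the SAE period is over. The footnote in the same section says that the event is recorded and analysed. If the site follows the sentence, the infant is still enrolled, has had an SAE inside the stated endpoint window, and appears in the SAE table as event-free.

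Whether a late SAE is captured then depends on two things that should not decide it: the date on which Visit 4 happened to fall, and the investigator's causality call. SAE occurrence is a named secondary endpoint, and each SAE goes to the IDMC (Protocol 5.4.1 and 5.4.2). The table would also claim an observation period that is longer than the one observed.

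**Working it through.** The plan gives no figure to reproduce, so this is date arithmetic on its own intervals.

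**Inputs**
- General SAE collection ends at last dose + 30 days (Protocol 8.2.1).
- Last dose to Visit 4: 21 to 48 days, optimum 30 (Tables 6 to 9).
- Longest allowed interval between doses: 78 days in the 2,4,6-month and 2-dose schedules, 48 days in the 2,3,4-month schedule (Tables 6 to 9).
- Latest formal End of Study: 8 months after the last subject's last visit (glossary).

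**Reading A: study end is Visit 4**

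Gap = max(0, Visit 4 day − 30), in days after the last dose.
- Visit 4 on day 21: the gap is 0, and collection runs 30 − 21 = 9 days beyond the endpoint window.
- Visit 4 on day 30: the gap is 0.
- Visit 4 on day 48: the gap is 48 − 30 = 18 days.

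The 18 days as a share of the longest allowed time from first dose to Visit 4:

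| Schedule | Longest window (days) | Share |
|---|---|---|
| 2,4,6 months | 78 + 78 + 48 = 204 | 18/204 = 8.8% |
| 2,3,4 months | 48 + 48 + 48 = 144 | 18/144 = 12.5% |
| 2 doses (2,4 or 3,5 months) | 78 + 48 = 126 | 18/126 = 14.3% |

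The share rises if the dose intervals are shorter. With optimal dose spacing and Visit 4 on day 48 it is 18/(60 + 60 + 48) = 18/168 = 10.7% for 2,4,6 months. For the other schedules it is 18/108 = 16.7%, where 108 = 30 + 30 + 48 or 60 + 48. The 18 days themselves do not change.

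The primary safety analysis uses the total vaccinated cohort (Protocol 10.8), which does not exclude infants seen after day 48. For them the gap exceeds 18 days.

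**Reading B: study end is the formal End of Study**

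Take 8 months as 8 × 30.4375 = 243.5 days and an infant whose Visit 4 is the last subject's last visit.
- Visit 4 on day 21: 21 + 243.5 − 30 = 234.5 days.
- Visit 4 on day 48: 48 + 243.5 − 30 = 261.5 days.

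This is an outer bound for that infant. The actual End of Study date is not given, and infants who finished earlier would have a longer gap.

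**Who is affected.** Under either reading, only SAEs judged unrelated (to the vaccine, to study participation and to a concurrent product of the sponsor) and not leading to withdrawal lose their collection rule at day 30. After discharge, Protocol 8.2.2 requires no active search for any SAE.

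**The case against.** The strongest reply is that this is a small wording mismatch. Much of it stands.

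- **A reader might infer that the endpoint runs to the last laboratory result, leaving months unobserved.** The documents do not support that as the intended meaning. Section 9.3 ties the end of the study to the study conclusion visit, Epoch 001 ends at Visit 4, and the last column of Tables 17 to 19 is the Visit 4 study conclusion. Section 8.4.1.1 has ongoing SAEs reviewed at later visits until the end of the study, which makes sense only for the individual infant. Section 11.5 uses the defined abbreviation when it means the formal date. Amendment 1 introduced that definition, and the endpoint in 10.2 carries no amendment mark.
- **A reader might infer that no SAE is collected after day 30.** That is wrong. The classes listed in 8.2.1 continue to discharge or have no day-30 limit, and Tables 4 and 5 make SAE recording at Visit 4 a required eCRF entry. The routine question to parents (8.2.3.1) covers the time since the last visit.
- **A reader might infer a bias between groups.** Nothing in the documents shows one. Both groups share the same rules, and all analyses are descriptive.
- The optimal Visit 4 is day 30 in every schedule, where the gap is zero. The documents do not say how many infants were seen later.
- The shading in Tables 17 to 19 could not be read, so the SAE bar may extend to Visit 4. Nothing here relies on it.
- Template titles may be adapted, so Template 21 adds little by itself.

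These points limit the size but do not remove the conflict. The Visit 4 recording entry and the footnote make the main sentence of 8.2.1 harder to apply. If the bar does reach Visit 4, it contradicts that sentence too.

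**Conclusion.** The point holds as a contradiction between stated rules. The main sentence of 8.2.1 ends general SAE collection at day 30 after the last dose. The endpoint, the SAP analysis and the table footnote go on to an end that the protocol uses in two senses.

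Taking Visit 4 as the end, the gap is 0 to 18 days within the allowed interval, or at most 8.8% to 14.3% of the longest allowed window depending on schedule. It is larger for any infant in the total vaccinated cohort seen after day 48. It exists only for infants seen after day 30 and only for SAEs judged unrelated that do not lead to withdrawal. The effect is a possible undercount of such SAEs. Its size in events cannot be estimated, because neither the spread of Visit 4 dates nor an SAE rate is given.

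The gap of roughly 8 months applies only if study end is taken to be the formal End of Study, which is the less likely reading. It is a reason to define the term, not an estimate of what is missed.

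**What to change.** Use one window everywhere: all SAEs, whatever the causality, from first dose to Visit 4 or day 30 after the last dose, whichever is later. Put that wording in Protocol 8.2.1, the footnotes to Tables 17 to 19, Protocol 10.2, SAP 4.2 and 6.4.1, and Template 21, in place of study end. Check the SAE bars in Tables 17 to 19 against it. Taking the later of the two dates also brings into the endpoint the up to 9 days of SAEs collected after an early Visit 4.

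The cost is small but is more than an edit to the SAP. Extending general SAE collection changes a protocol rule and needs an instruction to sites. In return it adds at most 18 days of recording of unrelated SAEs per infant within the allowed interval, at a visit that already records SAEs.

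The SAP already tabulates 601 infants by schedule, so a change to collection may come too late for some. In that case, label the endpoint and table with what was observed: all SAEs to day 30 after the last dose, and related SAEs to discharge. Aligning the endpoint wording with 8.2.1 in this way also removes the contradiction, but capture of late SAEs would still depend on the causality call.
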